- Approximately weekly, a patient presents to the UAMS Nuclear Medicine DEPT for a Sentinel Lymph Node (SLN) lymphoscintigraphy study. Classically, four injections of Technetium-99m (TC-99m) Sulfur Colloid (SC) are injected intra-dermally. The injections are in the immediate vicinity of a dermatologic malignancy or recent biopsy site. This allows identification of sentinel lymph nodes, in anticipation of surgical removal.

** The UAMS Nuclear Medicine DEPT does not do SLN injections of breasts **

- Pain during breast SLN procedures has been reported as high as 8.8/10 (1). Using Bicarbonate to alkalinize the radio-pharmaceutical injection, pain can safely be reduced from 6.6/10 to 4.7/10 during breast SLN procedures (2). There have been no discoverable studies assessing alkalinization to reduce pain during SLN procedures other than in the breast.

- It has been common practice in Emergency Rooms to buffer lidocaine at a ratio of 1:10 with Bicarbonate, to reduce the "chemical" pain from lidocaine's acidic nature. Similarly, Tc-99m SC is normally acidic with a pH of ~6.04 (2). Initial lab work reveals that a similar approach to altering the pH of Tc-99m SC should not significantly reduce the effectiveness of the Tc-99m SC. Alkalinization should significantly reduce the subjective pain.

Study Objectives

1. To quantify the reduction of perceived pain levels during SLN procedures, by altering the pH of the Tc-99m SC to near the physiologic value of 7.40.

Hypothesis

1. The perceived pain level during SLN techniques can be reduced by raising the pH of Tc-99m SC to near the physiologic level of pH 7.40.

Research Methods

1. Design: Randomized and double blinded prospective cross-over study.
2. After signing an informed consent, 60 serial subjects will undergo SLN injections and imaging as per normal routine—genitourinary, breast, and those requiring only a singular injection will be excluded.
3. The Tc-99m SC injections will have been randomized into two groups--- standard of care solution (unaltered) injected first and experimental solution (pH buffered with Sodium Bicarbonate) injected first.
4. A Nuclear Pharmacist will prepare the injections and label them such that the physician (not involved in the data assessment) performing the SLN injections is blinded as to which injections contain standard of care solution and which contain experimental solution.
5. Prior to beginning the procedure and after signing informed consent, the subject will be asked by a blinded research support assistant, to fill out a

Title: Does Alkalization of Technetium-99m Sulfur Colloid reduce perceived pain levels during non-breast sentinel lymphoscintigraphy?

PI: [name]

questionnaire addressing background information. Prior to beginning and after each injection, the subject will be asked to quantify the pain of each injection using a validated 0 through 10 scale, with 0 being no pain and 10 being severe pain that is disabling; unable to perform Activities of Daily Living.

III. Background and Rationale

- A. Approximately weekly, a patient presents to the UAMS NM DEPT for a SLN lymphoscintigraphy study. Classically, four injections of TC-99m SC are injected intra-dermally. The injections are in the immediate vicinity of a dermatologic malignancy or recent biopsy site. This allows for identification of SLNs, in anticipation of surgical removal. The UAMS NM DEPT does not do SLN injections of breasts.
- B. Pain during breast SLN procedures has been reported as high as 8.8/10 (1). Using Sodium Bicarbonate to alkalinize the radio-pharmaceutical injection, pain can safely be reduced from 6.6/10 to 4.7/10 during breast SLN procedures (2). There have been no discoverable studies assessing alkalinization to reduce pain during SLN procedures other than in the breast.
- C. It has been common practice in Emergency Rooms to buffer lidocaine at a ratio of 1:10 with Sodium Bicarbonate, to reduce the "chemical" pain from lidocaine's acidic nature. Similarly, Tc-99m SC is normally acidic with a pH of ~6.04 (2). Initial lab work reveals that a similar approach to altering the pH of Tc-99m SC should not significantly reduce the effectiveness of the Tc-99m SC.
- D. Alkalinization should significantly reduce the subjective pain experienced by patients undergoing SLN procedures at UAMS.

IV. Hypothesis and/or Specific Aims

- A. Hypothesis:
 1. The perceived pain level during SLN techniques can be reduced by raising the pH of Tc-99m SC to near the physiologic level of pH 7.40.
- B. Specific Aim:
 1. To quantify the reduction of perceived pain levels during SLN procedures, by altering the pH of the Tc-99m SC to near the physiologic value of 7.40.

V. Study Design and Procedures

- A. Design:
 1. Randomized, double blinded, and prospective cross-over design.
 2. Prior to beginning the procedure and after signing informed consent, 60 serial

Title: Does Alkalization of Technetium-99m Sulfur Colloid reduce perceived pain levels during non-breast sentinel lymphoscintigraphy?

PI: [name]

subjects will be asked by a blinded research support assistant, to fill out a questionnaire addressing background information. Before the first injection and after each injection, the subject will be asked to quantify the pain of each injection using a validated 0 through 10 scale, with 0 being no pain and 10 being severe pain that is disabling; unable to perform Activities of Daily Living.

3. Subjects will be randomized into one of two sequence groups (A & B):
 - a. Sequence group A. The first injection administered will be the standard of care solution (SOC). The second injection will be the pH altered solution. The remaining injections will be randomly assigned as either standard of care or pH altered.
 - b. Sequence group B. The first injection administered be the pH altered solution. The second injection will be the standard of care solution (opposite order). The remaining injections will be randomly assigned as either standard of care or pH altered.

Injection order for the two groupings which enrollees will be randomly assigned:

- Sequence group A: SOC, pH altered, random, random, random, etc.
 - Sequence group B: pH altered, SOC, random, random, etc.
4. A Nuclear Pharmacist will prepare the injections and label them such that the physician (not involved in the data assessment) performing the SLN injections is blinded as to which injections contain standard of care solution and which contain the pH altered solution. A planned dose range of 0.1 to 1.0 mCi will be used. The maximum activity injected will be 1.0 mCi with a maximum volume of 1.0 mL. Neither the addition of Sodium Bicarbonate nor the alteration of the pH result in any discernible change in the observable characteristics of the injectate---there is no clouding, there is no color change, there is no precipitate formation, etc.
 5. As per normal routine—genitourinary, breast, and those requiring only a singular injection will be excluded.

* The procedure for injection of Tc99m SC is currently being used as a diagnostic procedure and is in accordance with the community based standard of care. This study does not change the procedure; it only changes the pH of the solute being injected during a randomized number of injections.

* For the purposes of this study, the protocol is ended for each subject upon completion of the final pain assessment. The subjects will then continue on to the standard of care imaging and continued clinical management.

B. Survey instrument:

1. A questionnaire addressing pain quantity will be used. A validated 0 through 10 scale, with 0 being no pain and 10 being severe pain that is disabling; unable to perform Activities of Daily Living. Additionally, background

Title: Does Alkalization of Technetium-99m Sulfur Colloid reduce perceived pain levels during non-breast sentinel lymphoscintigraphy?

PI: [name]

information will be collected for subset analysis.

VI. Study Population

- A. Recruitment: Serial voluntary enrollment of 60 subjects.
- B. Study population: All patients, age 18 years and older, who present to UAMS NM DEPT for SLN evaluation.
- C. Inclusion criteria:
 1. Male and female patients of all races and ethnicities, age 18 years and older, presenting for SLN imaging for melanoma or who have had an excisional biopsy for melanoma of the thorax and appendicular structures;
 2. Patients scheduled to receive two or more injections of Tc-99m SC for the purpose of clinical management of melanoma or who have had an excisional biopsy for melanoma of the thorax and appendicular structures.
- D. Exclusion criteria:
 1. All patients presenting for SLN imaging of lesions involving the breast, ear, nose, and genitourinary regions;
 2. Patients scheduled to receive only a single injection of Tc-99m SC;
 3. All pregnant or breast feeding women. Women will be screened according to UAMS NM DEPT routine operating procedures prior to being considered for enrollment. Subsequently, only women who are found to be non-pregnant AND non-breast feeding will be invited for enrollment.

VII. Risks and Benefits

- A. Risks:
 1. Loss of patient personally identifiable information: In order to mitigate this, investigators shall maintain all personally identifiable information in accordance with UAMS policies. Moreover, only the primary investigator will have access to the code that identifies the subjects.
 2. Listed potential adverse reactions include:
 - a. For Tc-99m: Cardiopulmonary arrest, seizures, anaphylactic shock, hypotension, dyspnea, abdominal pain, fever, chills, bronchospasm, nausea, vomiting, perspiration, redness, urticaria, numbness, dizziness and burning at the injection site. Several deaths and cases of lung and soft tissue uptake other than RES have been reported in association with the use of Technetium Tc 99m Sulfur Colloid Injection.
 - b. For Sodium Bicarbonate: Chemical cellulitis.
- B. Benefits: Significantly less pain and suffering could potentially be experienced by future patients.

Title: Does Alkalization of Technetium-99m Sulfur Colloid reduce perceived pain levels during non-breast sentinel lymphoscintigraphy?

PI: [name]

VIII. Efficacy Assessments

- A. Prior to beginning and after each injection, subjects will be asked, by a blinded clinical assistant, to quantify the pain of each injection. Prior to beginning the injections, subjects will provide relevant background information by filling out a questionnaire.

IX. Safety Assessments

- A. Injection site pain of 8 out of 10 or less will not be considered an adverse event. Any adverse events will be appropriately documented and reported to the IRB in accordance with institutional policy.
- B. The principal investigator will assess the relationship of the adverse event to the investigational compound. The relationship will be assessed using the following categories:
 1. Definitely Related: A direct cause and effect relationship between the investigational compound and the adverse event exists.
 2. Possibly Related: A direct cause and effect relationship between the investigational compound and the adverse event has not been clearly demonstrated, but is likely or very likely.
 3. Unlikely Related: A direct cause and effect relationship between the investigational compound and the adverse event is improbable, but not impossible.
 4. Unrelated: The adverse event is definitely not associated with the investigational compound.

X. Data Handling and Recordkeeping

- A. Data form: A paper questionnaire to quantify the pain will be used. Additionally, it will collect background demographics---Appendix 1.
- B. The PI will carefully monitor study procedures to protect the safety of research subjects, the quality of the data and the integrity of the study. All study subject material will be assigned a unique identifying code or number. The key to the code will be kept in a locked file in the principal investigator's office. Only [name] or designated study staff will have access to the code and information that identifies the subject in this study.
- C. Upon completion of the study, all hard copy and electronic study records containing PHI will be destroyed or cleansed.

XI. Statistical Considerations

Title: Does Alkalization of Technetium-99m Sulfur Colloid reduce perceived pain levels during non-breast sentinel lymphoscintigraphy?

PI: [name]

- A. Planned Data Analysis: Reported pain responses to SOC and pH altered injections will be assessed using a basic cross-over design. Specifically, the two treatments will be studied within each subject; however, the sequence in which subjects will receive treatment will be randomized. Subjects randomized to one sequence group will receive the SOC injection first followed by the pH altered, while the other sequence group will receive pH altered then SOC injections. The following table succinctly presents this design.

Period	Sequence Group	
	A	B
1	SOC	pH altered
2	pH altered	SOC

In addition to the effect of treatment, the statistical model used to analyze this data must account for the effect of the sequence group, as well as the effect of *period*; therefore, the following mixed-effect analysis of variance model is proposed:

$$Y_{ijk} = \mu + \text{SEQ}_i + \text{sub}_{ij} + \text{PER}_k + \text{TRT}_h + e_{ijk}, \text{ where}$$

Y_{ijk} is the pain assessment for the j th subject during the k th period in the i th sequence group ($i = 1, 2$; $j = 1, 2, \dots, n_i$; $k = 1, 2$), SEQ_i is the effect of the i th sequence group, sub_{ij} is the effect of the j th subject in the i th sequence, PER_k is the effect of the k th period, TRT_h is the effect of the h th treatment ($h=1, 2$), and e_{ijk} is the error. The sequence, period and treatment effects will be modeled as fixed effects, while the subject effect and the error will be modeled random effects. An α -level of 5% will be used to determine the statistical significance of the treatment effect, as well as the other fixed effects.

One potential shortcoming of the proposed cross-over design is that the pain assessments will be made within minutes of one another; thus, a period or “carry-over” effect may be present. The proposed model will be able to detect such effects and, if present, only data from the first period will be used to evaluate the effect of treatment. In this case, the model reduces to a simple two-sample t-test.

- B. Sample Size Justification: We wish the study to be sufficiently powered in the event that a significant “carry-over” or period effect is detected and only the first period data is used to evaluate the effect of treatment. To this end, the following sample size calculation is based on a two-sample t-test. A recent study by Stojadinovic et al. reported a pain scale standard deviation of 2.65 for a SOC group. We anticipate that the pH adjusted group will reduce pain, on average, by 2 points. Given this information, a two-sample t-test will have over 80% power to detect this difference assuming 30 subjects per group (60 in total) are enrolled. (It should be noted that if no carry-over effect is detected and both periods are

Title: Does Alkalization of Technetium-99m Sulfur Colloid reduce perceived pain levels during non-breast sentinel lymphoscintigraphy?

PI: [name]

used in the analysis, the proposed sample size will provide the test of the treatment effect with over 98% power to detect a 2 point difference and with over 80% power to detect a 1 point difference).

C. Randomization: To ensure the number of subjects randomly assigned to each sequence group is equal, the technique of permuted block randomization will be employed. The randomization procedure will also be stratified according to the following, broadly defined sites of injection:

1. Thorax, including neck and buttocks;
2. Head;
3. Appendicular structures, including shoulder to wrist, including back of hand, and hip to ankle;
4. Other (remainder of hand and feet).

Randomization will be applied independently within each stratum. That is, a separate randomization “schedule” will be applied within each stratum. This will ensure that the injection site distribution of the sequence groups will be similar.

XII. Ethical Considerations

- A. This study will be conducted in accordance with all applicable government regulations and University of Arkansas for Medical Sciences research policies and procedures. This protocol and any amendments will be submitted and approved by the UAMS Institutional Review Board (IRB) to conduct the study.
- B. The formal consent of each subject, using the IRB-approved consent form, will be obtained before that subject is submitted to any study procedure. All subjects for this study will be provided a consent form describing this study and providing sufficient information in language suitable for subjects to make an informed decision about their participation in this study. The person obtaining consent will thoroughly explain each element of the document and outline the risks and benefits and alternate treatment(s). The consent process will take place in a quiet and private room, and subjects may take as much time as needed to make a decision about their trial participation. Participation privacy will be maintained and questions regarding participation will be answered. No coercion or undue influence will be used in the consent process. This consent form must be signed by the subject or legally acceptable surrogate, and the investigator-designated research professional obtaining the consent. A copy of the signed consent will be given to the participant, and the informed consent process will be documented in each subject's research record.

Title: Does Alkalization of Technetium-99m Sulfur Colloid reduce perceived pain levels during non-breast sentinel lymphoscintigraphy?

PI: [name]

- C. At any time during the clinical encounter, any participant may opt out of the study by providing written direction or by simply verbally communicating to any staff member that the participant no longer wishes to be enrolled in the study. At that time, the participant would be no longer enrolled in the study, and the remainder of their care would only be that of the routine standard of care, without bias.
- D. In the event that a participant reports pain associated with the procedure and requests analgesia, no analgesia will be provided by the UAMS NM DEPT. None is provided as the standard of care in day-to-day routine.

XIII. Quality Control and Quality Assurance

- A. Industry standard quality control tests have already been run on initial bench work versions---all tests passed quality control appropriately.

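### No rating of present pain precedes injection 2, so residual pain cannot be told from an order effect, and the sequence test has only about 12–17% power for a 1-point differential carry-over

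*Combined protocol and SAP*

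**What the plan says.** - **Ratings.** Section V.A.2: "Before the first injection and after each injection, the subject will be asked to quantify the pain of each injection". Section VIII.A has the same schedule: "Prior to beginning and after each injection, subjects will be asked, by a blinded clinical assistant, to quantify the pain of each injection". Research Methods item 5 in the opening summary agrees. No section names a rating of present pain just before injection 2, and none gives a minimum interval between injections.
- **Interval.** Section XI.A concedes that "the pain assessments will be made within minutes of one another" and names a possible period or carry-over effect.
- **Model.** "The sequence, period and treatment effects will be modeled as fixed effects", with subject random. There is no baseline covariate and no separate carry-over term. The alpha "level of 5% will be used to determine the statistical significance of the treatment effect, as well as the other fixed effects".
- **Rule.** "The proposed model will be able to detect such effects and, if present, only data from the first period will be used" to judge the treatment. Section XI.B sizes the trial, at 30 per group, for that fallback.

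**The concern.** The plan foresees that pain from injection 1 may still be present when injection 2 is rated, but it collects nothing that would show this directly. It relies on the model instead.

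The model offers two indirect signals. The sequence contrast responds to carry-over that differs between the solutions, but it is a between-subject comparison with little power. The period contrast is sensitive, but it responds equally to residual pain and to any ordinary order effect, such as a second injection feeling worse because the first has been experienced. An ordinary order effect does no harm, because the PER term already adjusts for it.

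At stake are a modest understatement of the reduction the trial sets out to quantify and, more likely, the needless loss of period 2. In either case the data could not show afterwards which had happened.

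**Working it through.** **Inputs.** From section XI.B: 30 per sequence group, a 2-point difference, and an SD from a study that "reported a pain scale standard deviation of 2.65 for a SOC group". From XI.A: a 5% level, taken as two-sided because sidedness is not stated. To scale residual pain, the SOC mean is set at 6.6, the breast figure cited in III.B (the plan states no expected means of its own), and the buffered mean at 6.6 − 2 = 4.6. Two quantities are not in the documents and are assumed: the within-subject correlation ρ (0 to 0.7), and f, the fraction of mean injection 1 pain added to the injection 2 score. Scores are treated as normal, with no ceiling.

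**1. The plan's own power.** For period 1 only, SE = 2.65 × √(2/30) = 0.684. Noncentral t on 58 df gives 82.0% for 2 points, which agrees with the stated figure of over 80%. For both periods, SE = 2.65 × √(2(1 − ρ)/60). At ρ = 0 this is 0.484, with 98.2% power for 2 points. At ρ = 0.5 it is 0.342, with 82.0% power for 1 point. The stated 80% for 1 point needs ρ of about 0.47 or more, so 0.5 serves as the central value.

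**2. Where carry-over appears.** Let τ be SOC minus buffered, π the order effect, and c_S and c_B the residual pain after SOC and after buffered, with λ = c_S − c_B.
- Group A, injection 1 minus injection 2: τ − π − c_S.
- Group B, injection 1 minus injection 2: −τ − π − c_B.
- Half the difference between groups, the treatment estimate: τ − λ/2.
- Period contrast: π + (c_S + c_B)/2, so order effect and mean residual are confounded.
- Sequence contrast of subject totals: λ. This is the only place where λ can be tested.

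**3. Power of the sequence test.** SE = 2.65 × √(2(1 + ρ)) × √(2/30).

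| ρ | SE | Power, λ = 1 |
|---|---|---|
| 0 | 0.968 | 17% |
| 0.5 | 1.185 | 13% |
| 0.7 | 1.262 | 12% |

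**4. The whole rule, simulated** (20,000 trials per setting, ρ = 0.5, τ = 2, λ = 2f, no true order effect).

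| f | Sequence test fires | Period test fires | Either fires | Two-period estimate | Mean estimate reported |
|---|---|---|---|---|---|
| 0.10 | 5% | 36% | 40% | 1.90 | 1.95 |
| 0.15 | 6% | 67% | 69% | 1.84 | 1.96 |
| 0.20 | 6% | 90% | 90% | 1.80 | 1.98 |
| 0.25 | 7% | 98% | 98% | 1.76 | 2.00 |
| 0.50 | 13% | 100% | 100% | 1.50 | 1.99 |

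Across ρ from 0 to 0.7, the average shortfall of the reported estimate is at most about 0.07 points.

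**5. Residual masked by an opposite order effect.** If the order effect is −f × (6.6 + 4.6)/2 = −5.6f, the period contrast is zero on average. At f = 0.10 and 0.50 either test then fires in only 10% and 18% of trials, and the mean reported estimates are 1.93 and 1.70. The shortfall at f = 0.50 is 2 − 1.70 = 0.30.

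**6. Harmless order effect of 1 point, no residual.** The period test has the same SE as the two-period treatment contrast. It fires in 53% of trials at ρ = 0, 82% at ρ = 0.5 and 96% at ρ = 0.7. Once it fires, at ρ = 0.5 the SE goes from 0.342 to 0.684, the 95% half-width from about 0.7 to 1.4 points, and power for 2 points from over 99% to 82%.

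**7. What a direct rating adds.** Take f = 0.5 and the cited breast difference of 6.6 − 4.7 = 1.9. Residual pain before injection 2 then differs by 0.5 × 1.9 = 0.95 between groups. With an assumed residual SD of 1 to 2, comparing that rating between groups has 95% to 44% power. The sequence test has 12–16% for the same difference.

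**The case against.** A reader might infer that residual pain would pass unseen and that a clearly attenuated estimate would be published. The documents do not support that. Section XI.A makes a period effect as well as a carry-over effect a reason to use period 1 only. Residual pain raises injection 2 scores in both sequence groups, so the sensitive period test picks it up. Period 1 cannot contain pain from an earlier study injection, and XI.B gives it over 80% power, which reproduces. The two-period values of 1.76 and 1.50 in step 4 are therefore almost never the ones reported. With no treatment effect, residual pain proportional to injection 1 pain is equal in the two groups, so it creates no false benefit.

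It is also fair to say that subjects are already asked for the pain of each injection, that the questionnaire (Appendix 1) is a separate document not available here, and that f and ρ are assumptions. At f = 0.5 the SOC mean at injection 2 would be 6.6 + 0.5 × 4.6 = 8.9, close enough to 10 for an additive model to be strained.

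All of this stands, and it limits the harm. It does not answer two points. The period test cannot say why it fired, and the general claim of detectability is not true of differential carry-over.

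**Conclusion.** The point holds as an inexpensive improvement to measurement and the correction of one overstated property; it does not show that the result would be seriously biased.

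- **Detection.** Differential carry-over of 1 point would be found about 12–17% of the time.
- **Bias.** The period test usually sends the analysis to period 1 once residual pain reaches about 15–25% of injection 1 pain. Averaged over trials, the undetected shortfall is at most about 0.07 points. It reaches about 0.3 points at f = 0.5 only if an opposite order effect hides the residual.
- **Precision.** The likelier cost is discarding period 2 for a harmless order effect: 53–96% of trials for a 1-point effect, with the confidence interval twice as wide at ρ = 0.5.

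These sizes rest on the assumed ρ and f, additive residual pain, no ceiling, and pain levels taken from the cited breast figures. The gap in the rating schedule and the confounding of residual pain with order do not depend on them.

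**What to change.** 1. In V.A.2 and VIII.A, ask the same 0–10 question about pain present at that moment immediately before every injection, not only the first. Match this in Research Methods item 5 and on the form.
2. In XI.A, report pre-injection-2 pain by sequence group as the direct evidence on residual pain, and state that a period effect alone is not read as carry-over, because PER already adjusts for it.
3. In XI.A, replace the statement that "The proposed model will be able to detect such effects" with one saying that the sequence test has low power for differential carry-over at this sample size.

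The cost is one extra verbal rating per injection by the same blinded assistant, one column on the paper form, and a few lines of protocol text. Repeated questioning may draw some attention to pain, equally for both solutions. The rating captures residual pain only, not other forms of carry-over, and it cannot be recovered once a session is over.

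### Pain is scored after every randomised injection, but the analysis model has only two periods, so about half of a typical subject's scores have no stated use

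*Combined protocol and SAP*

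**What the plan says.** - **Allocation (V.A.3).** Each sequence group starts with one injection of each solution. For the rest, "The remaining injections will be randomly assigned as either standard of care or pH altered". The layouts are "Sequence group A: SOC, pH altered, random, random, random, etc" and "Sequence group B: pH altered, SOC, random, random, etc". No probability or balance rule is given for the random part. The permuted blocks in XI.C concern the sequence group only.
- **Number of injections.** Section III.A: "Classically, four injections of TC-99m SC are injected intra-dermally". Eligibility (VI.C.2) covers "Patients scheduled to receive two or more injections of Tc-99m SC", so the number varies.
- **Data collected (V.A.2).** "Before the first injection and after each injection, the subject will be asked to quantify the pain of each injection".
- **Model (XI.A).** The response "is the pain assessment for the j th subject during the k th period in the i th sequence group", with k limited to 1 and 2. Sequence, period and treatment are fixed effects and subject is random. The design table shows two periods.
- **Carry-over (XI.A).** The section says that the model can detect a period or carry-over effect and that, "if present, only data from the first period will be used to evaluate the effect of treatment".
- **Sample size (XI.B).** The size of 60 rests on the first-period comparison: difference 2, SD 2.65, 30 per group, power over 80%. With both periods it claims over 98% power for 2 points and over 80% for 1 point.

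**The concern.** A subject with four injections gives four scores under randomised allocation, and the model has room for two. The plan does not say whether the others are secondary, exploratory or unused.

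The omission matters most where the plan is most worried. Section XI.A names carry-over between injections minutes apart as the weakness of the design, and its answer is to drop to one score per subject. The later injections are what would allow carry-over to be estimated separately and the treatment effect to be adjusted for it. A period effect on its own is no reason to discard data, because the model already contains a period term.

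At stake are the precision of the primary estimate and the ability to deal with carry-over without giving up the within-subject comparison.

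**Working it through.** **Inputs.** N = 60, 30 per group, SD 2.65, differences of 2 and 1 points (XI.B); four injections (III.A); two-sided 5% (XI.A gives 5%; two-sided is assumed). Also assumed, because the documents do not give them: within-subject correlation ρ (0.5, range 0.3 to 0.7), independent 50:50 assignment of injections 3 and 4, and four injections for everyone.

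**1. The plan's own figures.** First period only: SE = 2.65 × √(2/30) = 0.684. The noncentral t gives 82.0% power for 2 points, in line with XI.B. Both periods: SE = 2.65 × √(2(1 − ρ)/60). At ρ = 0 power for 2 points is 98.2%. For 1 point it is 52.9% at ρ = 0 and 82.0% at ρ = 0.5. The plan's 1-point claim therefore already implies a correlation of about 0.5.

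**2. Why two periods cannot show carry-over.** Code treatment t = ±½ and carry-over c as the previous injection's t (0 for injection 1). For the first pair in a group with sign s, t = (s/2, −s/2), the sequence column is (s/2, s/2) and c = (0, s/2). So c = (sequence − t)/2 exactly. With sequence and treatment in the model, a carry-over term cannot be estimated.

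**3. Treatment SE using all four injections, existing allocation.** Let σ = 2.65√(1 − ρ) and w = ρ/(1 − ρ + 4ρ). Average information per subject, in units of 1/σ², is E[Σt²] − w·E[(Σt)²]. Here Σt² = 1. Σt is ±1 for a 3:1 split (probability ½) and 0 for 2:2, so E[(Σt)²] = 0.5.

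At ρ = 0.5: σ = 1.874, w = 0.2, information = 1 − 0.2 × 0.5 = 0.9, SE = 1.874/√(60 × 0.9) = **0.255**. Injections 1 and 2 alone: information 0.5, SE = 1.874/√30 = **0.342**.

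**4. Adding first-order carry-over.** E[Σtc] = −0.25, E[Σt·Σc] = 0.25, E[Σc²] = 0.75 and E[(Σc)²] = 0.25. The cross term is −0.25 − 0.2 × 0.25 = −0.30, and the carry-over term is 0.75 − 0.2 × 0.25 = 0.70. Remaining treatment information is 0.9 − 0.30²/0.70 = 0.771, so SE = 1.874/√(60 × 0.771) = **0.275**. The plan's sequence term can stay: Σt and Σc depend only on the freely randomised injections, so these SEs do not change.

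| Treatment SE (points) | ρ = 0.3 | ρ = 0.5 | ρ = 0.7 |
|---|---|---|---|
| First period only | 0.684 | 0.684 | 0.684 |
| Injections 1 and 2 | 0.405 | 0.342 | 0.265 |
| All four | 0.298 | 0.255 | 0.199 |
| All four, with carry-over term | 0.319 | 0.275 | 0.216 |

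In power for 1 point at ρ = 0.5, by Φ(1/SE − 1.96): 83% from injections 1 and 2, 97.5% from all four, 95% with the carry-over term.

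**5. Fewer injections.** If everyone had three (ρ = 0.5, w = 0.25), information is 0.75 − 0.25 × 0.25 = 0.6875 and SE = 1.874/√(60 × 0.6875) = 0.292. With carry-over it is 0.6875 − 0.25²/0.5 = 0.5625 and SE = 0.323. Subjects with two injections add nothing beyond the current model.

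**The case against.** The best defence is that the plan is adequate without these scores. It is sized on its least efficient analysis and reaches 82% power there for the 2 points it expects. The first-period comparison needs no assumption about carry-over, whereas the longer model assumes that carry-over lasts one injection and adds to the treatment effect. The first part stands: a reader might infer that the trial is underpowered, and XI.B does not support that. The second part stands as a cost. It is a reason for a sensitivity analysis, not for leaving collected, randomised data without a role.

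A reader might also infer that the free randomisation of injections 3 onward is itself the fault, since half of four-injection subjects would get a 3:1 split under 50:50 assignment, and that a mirrored order (SOC, pH, pH, SOC and its opposite) would be better throughout at no cost. The documents do not support this:

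- Under the two-period model in XI.A, the order of injections 3 and 4 changes nothing; the SE is 0.342 either way.
- Once all four are analysed, mirroring lowers the SE from 0.255 to 0.242 (about 5%), or from 0.275 to 0.254 with first-order carry-over (about 8%). At a correlation of 0 the treatment SE does not improve.
- If carry-over lasts two injections, mirroring is clearly worse: treatment SE about 0.38 against 0.28 at ρ = 0.5. With scores minutes apart, that cannot be excluded.
- Mirroring leaves two possible sequences, so one identified syringe reveals all the others. Section V.A.4 says that the solutions look alike, but the score is subjective and the pain response may itself be a cue. At present syringe 2 follows from syringe 1, while later ones stay unpredictable.

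Mirroring is therefore a trade-off, and the present allocation is a defensible choice.

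**Conclusion.** The point holds as a gap in the analysis plan. For a subject with four injections, two of the four scores have no stated use, and the two-period model cannot separate carry-over from sequence. Using all scores under the existing allocation cuts the treatment SE by about a quarter (0.342 to 0.255), or by about a fifth with carry-over adjustment (0.275). Against the fallback of 0.684, the adjusted SE is about 40% as large.

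The sizes rest on four injections for all 60 subjects, independent 50:50 assignment, SD 2.65 at every injection, an equal correlation between any two scores of a subject, and first-order carry-over. The direction is the same at correlations 0.3 to 0.7; the gain is smaller where subjects have fewer injections. The plan does not say that the later scores will be discarded, only nothing about them.

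**What to change.** In XI.A:

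1. Let k run over all injections that a subject receives. Use injection order as the period effect, subject as a random effect, the solution given as treatment, and add a term for the previous solution (zero for the first injection).
2. Replace the rule that falls back to first-period data with the carry-over-adjusted estimate from this model. If that rule stays, a detected effect would discard all the added data.
3. Name an analysis of injections 1 and 2 as a sensitivity analysis, to check the assumed form of carry-over.

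In V.A.3, keep the free randomisation of later injections and state its probability, because the precision figures depend on it. Update the two-period power statement in XI.B to match.

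The cost is a few lines of text and one further modelling assumption. No patient, syringe or assessment is added.
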